5 TREATMENT PLAN

Each patient can receive a maximum of 6 cycles of study treatment. Each treatment cycle will last 4 weeks (28 days) and a delay up to day 42 is allowed if necessary to meet eligibility criteria for starting subsequent cycles. Patients will be stratified into two groups for response analysis purposes:

Table 1: Treatment Plan for all Patients

INDUCTION			MAINTENANCE			
Cycle						
1	2		3	4	5	6
Clofarabine 25 mg/m ² /day Days 1-5 I.V. 2 hrs +/- 30 min		Disease Evaluation	Clofarabine 25 mg/m ² /day Days 1-5 I.V. 2 hrs +/- 30 min			

Induction: Clofarabine on Days 1-5 of each cycle, administered as I.V. infusion at 25 mg/m²/day. No drug treatment from Day 6 to Day 28. This cycle will be repeated once.

Evaluation of disease response (see Section 9) will be performed after 2 cycles of Induction Therapy. In the absence of disease progression, participants will be eligible to receive up to 4 cycles of Maintenance Therapy, which is identical to the Induction Therapy.

Maintenance: Clofarabine on Days 1-5 of each cycle, administered as I.V. infusion at 25 mg/m²/day. No drug treatment from Day 6 to Day 28. Cycle will be repeated for up to three more times every 28 days.

CONFIDENTIAL

This document is confidential. Do not disclose or use except as authorized.

Treatment may be administered on an outpatient basis. Expected toxicities and potential risks as well as dose modifications for clofarabine is described in Section 6. No investigational or commercial agents or therapies other than those described below may be administered with the intent to treat the participant's malignancy.

5.1 Criteria to Proceed with Cycle 1

The following assessment must be completed within 3 days prior to starting Cycle 1. **Patients need to re-meet lab eligibility criteria as described in section 3.1.**

1. Complete physical examination including height, weight and BSA.
2. Performance status $\geq 70\%$ (use Lansky score for age < 16 and Karnofsky score for age ≥ 16 , see Appendix I).
3. Concurrent medical conditions.
4. Hematology: CBC with differential and platelet count and peripheral blood smear.
5. Serum chemistries: Electrolytes (calcium, magnesium, phosphorus, sodium, potassium, chloride, and bicarbonate), blood urea nitrogen (BUN), creatinine, and serum glucose. Liver function tests (total protein/albumin, aspartate aminotransferase (AST), alanine aminotransferase (ALT), alkaline phosphatase (ALP), total bilirubin).
6. Uric Acid as clinically indicated.
7. Urinalysis.
8. Baseline adverse event assessment from time of signing informed consent.

5.2 Criteria to Proceed with Subsequent Cycles

A treatment cycle will be repeated every 28 days (or no more than 42 days) if the participant does not have disease progression and any non-hematologic toxicities have recovered to grade 1 or become a tolerable grade 2, except those grade 3 toxicities specified in section 6.3.2.

The following assessment must be completed within 3 days prior to starting all subsequent cycles. **Patients need to re-meet lab eligibility criteria as described in section 3.1.**

1. Complete physical examination including height, weight and BSA.
2. Performance status $\geq 70\%$ (use Lansky score for age < 16 and Karnofsky score for age ≥ 16 , see Appendix I).
3. Hematology: CBC with differential and platelet count and peripheral blood smear.
4. Serum chemistries: Electrolytes (calcium, magnesium, phosphorus, sodium, potassium, chloride, and bicarbonate), blood urea nitrogen (BUN), creatinine, and serum glucose. Liver function tests (total protein/albumin, aspartate aminotransferase (AST), alanine aminotransferase (ALT), alkaline phosphatase (ALP), total bilirubin).

CONFIDENTIAL

This document is confidential. Do not disclose or use except as authorized.

5. Uric Acid as clinically indicated.
6. Urinalysis.
7. Concomitant Medications/Transfusions.
8. Adverse event assessment.

5.3 Drug Administration

Clofarabine should be diluted with NS or D5W prior to administering by IV infusion over 2 hours (+/- 30 minutes). The dosage is based on the participant's body surface area (BSA), calculated using the actual height and weight obtained on the day of treatment or at least within three days before the start of each cycle. To prevent drug incompatibilities, no other medications should be administered through the same IV line.

Participants may receive hydration per institutional standards during clofarabine treatment, giving careful consideration to the cardiac and renal function of the participant. Hyperhydration is not required.

5.4 General Concomitant Medication and Supportive Care Guidelines

5.4.1 Prophylactic Steroid Administration

Prophylactic steroid (i.e. hydrocortisone or dexamethasone) has been administered by some investigators in investigator sponsored clinical studies with clofarabine and has been reported to minimize the occurrence and/or severity of the following potential clofarabine-related toxicities: nausea, vomiting, skin rash/desquamation, and capillary leak syndrome.

5.4.2 Management of Capillary Leak Syndrome

In previous studies, during or shortly after IV clofarabine administration a few participants developed signs and symptoms consistent with capillary leak syndrome. In these heavily pretreated participants, it has been difficult to separate potential drug-related cases of capillary leak syndrome from concurrent medical conditions such as infection/sepsis, progressive disease, or other underlying problems resulting from prior antileukemic therapies.

For these reasons, during and after each dose of clofarabine, the onset of the following signs or symptoms \geq grade 2 will be assessed:

- Tachypnea or other evidence of respiratory distress;
- Unexplained hypotension; and/or
- Unexplained tachycardia.

If one or more of these signs or symptoms occur during study drug infusion, clofarabine administration will be interrupted or held as clinically indicated. It is recognized that the total infusion time for this clofarabine dose in this circumstance may exceed 2 hours. Thus, if the

CONFIDENTIAL

This document is confidential. Do not disclose or use except as authorized.

participant's condition stabilizes or improves, clofarabine administration may resume. Pretreatment (30-60 minutes prior to clofarabine administration) with steroids (e.g. hydrocortisone 50-100 mg/m²/day for up to 3 days or its equivalent, or dexamethasone 5-10 mg/m²/day) is recommended for all subsequent doses during the remainder of that treatment cycle and for all subsequent treatment cycles.

5.4.3 Anti-Emetics

Clofarabine is moderately emetogenic. Therefore, standard anti-emetic therapy (such as prochlorperazine or a 5HT₃ antagonist, or/and dexamethasone) should be administered prior to therapy.

5.4.4 Blood Products

All blood products are to be irradiated and leukocyte-reduced according to each institution's guidelines. Also, CMV-negative participants should receive CMV-negative blood products according to each institution's guidelines.

5.4.5 Infection Prophylaxis

The use of prophylactic antibacterial, antifungals, and antiviral agents is recommended according to each institution's guidelines.

5.4.6 Treatment of Fever and Neutropenia

Treatment of fever and neutropenia should follow institutional guidelines.

5.4.7 Colony Stimulating Factors

Participants experiencing prolonged neutropenia (ANC < 500/mm³ for > 7 days) may receive myeloid growth factor support (filgrastim or peg-filgrastim). For subsequent cycles, growth factor support should be administered starting at least 24 hours after the last dose of clofarabine, and if administered daily, until ANC > 1,500/mm³ after expected decrease in neutrophil counts.

5.4.8 Concomitant Therapy

No concomitant cytotoxic therapy or investigational therapy is allowed during the study.

Clofarabine is excreted primarily by the kidneys. Therefore, drugs with known renal toxicity (e.g. vancomycin, amphotericin B, acyclovir, cyclosporin, methotrexate, tacrolimus) should be avoided to the extent possible during the 5 days of clofarabine treatment in each cycle or, if required, administered cautiously and with close monitoring. Additionally, the liver is a known target organ for clofarabine toxicity. Therefore, concomitant use of medications known to induce hepatic toxicity (e.g., voriconazole, cyclosporine, methotrexate, tacrolimus) should be avoided to the extent possible or, if required, administered cautiously and with close monitoring. Hepatic and renal

CONFIDENTIAL

This document is confidential. Do not disclose or use except as authorized.

function should be assessed prior to and during treatment with clofarabine and it is recommended that the participant's fluid status and hepatic and renal function be carefully monitored during the drug administration period. Use of alternative medications (e.g., herbal or botanical for anticancer purposes) is not permitted during the entire study period.

5.5 Duration of Therapy

Duration of therapy will depend on individual response, evidence of disease progression and tolerance. In the absence of treatment delays due to adverse events, treatment may continue for a maximum of 6 cycles of study treatment or until one of the criteria for removal from protocol therapy (section 5.7) applies.

5.6 Duration of Follow Up

After completion of protocol therapy or removal from protocol therapy, participants will be followed for 3 years, or until death, whichever occurs first. Follow-up studies should be done annually at 12, 24, and 36 months after therapy (see Table 2 for scheduled tests).

5.7 Criteria for Removal from Protocol Therapy

Participants will be removed from protocol therapy when they have not met eligibility criteria for starting subsequent cycles as defined in section 5.2 by end of cycle 2, or if they have met any of the criteria listed below:

- Disease progression or death
 - Participants who experience disease progression that requires systemic therapy will be followed for survival, disease status and subsequent treatment for 3 years, but will not be required to complete any other protocol-defined follow-up assessments.
- Intercurrent illness that prevents further administration of treatment
- Second malignancy
- Unacceptable adverse event(s)
- Participant demonstrates an inability or unwillingness to comply with the medication regimen and/or documentation requirements
- Participant decides to withdraw from the study
- General or specific changes in the participant's condition render the participant unacceptable for further treatment in the opinion of the treating investigator.
- The participant becomes pregnant or fails to use adequate birth control if able to conceive

The reason for removal from protocol therapy and the date the participant is removed must be documented in the study-specific case report form (CRF). Alternative care options will be discussed with the participant.

CONFIDENTIAL

This document is confidential. Do not disclose or use except as authorized.

Documentation of why the patient was removed from treatment and if the patient wishes to continue to be followed is required. This documentation needs to be sent to the DFCI Study team within 7 days of the patient being removed from treatment, if they are coming off treatment early.

For Decentralized Subject Registrations, the research team updates the relevant Off Treatment/Off Study information in OnCore.

In the event of unusual or life-threatening complications, or any change of on study status, participating investigators must immediately notify the Principal Investigator (or Protocol Chair), [name] at [contact] and e-mail the Lead Institution clinical research coordinator listed on the first page of this protocol.

5.8 Criteria for Removal from Study

Participants will be removed from the study for the following reasons:

- a) Completion of 3-year follow-up period
- b) Death
- c) Lost to follow-up
- d) Withdrawal of consent for data submission
- e) Study completion

6 DOSE DELAYS/DOSE MODIFICATIONS

Dose delays and modifications will be made using the following recommendations. Toxicity assessments will be done using the CTEP Version 4.0 of the NCI Common Terminology Criteria for Adverse Events (CTCAE) which is identified and located on the CTEP website at:

http://ctep.cancer.gov/protocolDevelopment/electronic_applications/ctc.htm.

If possible, symptoms should be managed symptomatically. In the case of toxicity, appropriate medical treatment should be used (including anti-emetics, anti-diarrheas, etc.).

All adverse events experienced by participants will be collected from the time of the first dose of study treatment, through the study and up to 30 days from the last dose of treatment. Participants experiencing toxicities that are possibly related to the study treatment at the off-study visit will be followed up until the conditions resolved or clinically stabilized.

6.1 Anticipated Toxicities

For detailed information on clofarabine toxicology refer to the Investigator's Brochure for clofarabine.⁶⁷

CONFIDENTIAL

This document is confidential. Do not disclose or use except as authorized.

6.1.1 Toxicity

Adult Patients

Drug-related AEs observed in at least 10% of adult participants treated with clofarabine in previous clinical trials include myelosuppression, nausea, vomiting, infections, fatigue, headache, diarrhea, rigors, dermatitis, anorexia, febrile neutropenia, myalgia, asthenia, petechiae, transient elevated liver enzymes, stomatitis, mucositis, pyrexia, flushing, constipation, edema, dehydration, nervousness, stomach pain, insomnia, depression, dry skin, back pain, and decreased weight.⁸

Adverse events reported in <10% of adult participants include tumor lysis syndrome, capillary leak syndrome, palmar plantar erythrodysesthesia, pancreatitis, seizures, irregular heartbeat, edema, pericardial effusion, multi-organ failure, and death.⁸

Pediatric Patients

The most common side effects observed in previous clinical studies of pediatric patients treated with clofarabine 52 mg/m² include vomiting NOS, nausea, febrile neutropenia, diarrhea NOS, headache NOS, pruritus NOS, pyrexia, dermatitis NOS, fatigue, rigors, abdominal pain NOS, tachycardia NOS, anorexia, petechiae, epistaxis, pain in limb, hypotension NOS, anxiety NEC, cough, constipation, erythema NEC, mucosal inflammation NOS, pain NOS, flushing, edema NOS, and hematuria.⁸

Pediatric patients have also experienced increased liver enzymes and increased creatinine. Moderate neurological changes have been reported in some patients. Infections were reported in almost half of the patients treated with clofarabine.

Other potential SAEs include pericardial effusion, LVSD, tumor lysis syndrome, SIRS, and capillary leak syndrome.⁸

Sanofi US Services Inc., on behalf of itself, and its affiliate, Genzyme Corporation is conducting a Phase I/II study to assess concomitant use of clofarabine, etoposide and cyclophosphamide in pediatric patients with acute leukemias. In the Phase I portion of the study, febrile neutropenia, pyrexia and neutropenia were the most commonly reported serious adverse events and were reported in 64%, 20%, and 16% of patients, respectively. There were 10 patient deaths in the trial (malignant disease, n=5; adverse events, n=2: infection/micrococcus meningitis, CNS hemorrhage; and other causes, n=3: intracranial hemorrhage, multi-organ failure, unknown etiology). Dose-limiting toxicities included a grade 3 elevation of lipase, abdominal pain and possible veno-occlusive disease (VOD) that resolved (cohort 3) and 1 case of prolonged bone marrow aplasia (cohort 5). In the Phase II portion 3 of the 4 first patients treated reported veno-occlusive disease (VOD) symptoms including hyperbilirubinemia, hepatomegaly, right upper quadrant pain, ascites and/or weight gain. VOD-like signs and symptoms initially presented within 5 to 12 days of the first dose of clofarabine in these patients. Two of the patients with VOD symptomatology had a history of HSCT and total body irradiation (TBI) within the previous 4 to 7 months.³ All 3 patients with VOD-like symptoms had ongoing severe infections and/or capillary leak syndrome preceding the occurrence of hepatotoxicity. The fourth patient reported grade 4 hyperbilirubinemia and had a history of HSCT and TBI greater than 1 year prior to study entry. As a result of these safety

CONFIDENTIAL

This document is confidential. Do not disclose or use except as authorized.

findings, the updated protocol now states that patients with a history of prior HSCT, elevated conjugated serum bilirubin at study entry, uncontrolled systemic fungal, bacterial, or other infection, a history of hepatitis B or C infection or a history of cirrhosis are to be excluded from study participation. The warnings and precautions section of the Clofarabine (Clolar) package insert has also been revised to reflect the recent safety findings.⁸

6.2 Toxicity Management

Please refer to section 5.4 (General Concomitant Medication and Supportive Care Guidelines) for management of toxicity.

6.3 Dose Modifications/Delays

6.3.1 Hematologic Toxicity

- Participants who experience prolonged neutropenia ($ANC < 500/\mu L$ for > 7 days) may receive growth factor support (see 5.3.7). If neutropenia persists ($ANC < 500/\mu L$) despite the addition of growth factor support and in the absence of hematopoietic involvement by Histiocytosis, but recovered by day 42 of the cycle, the subsequent cycle may start at a reduced dose of clofarabine by 25%. If prolonged neutropenia ($ANC < 500/\mu L$ for > 7 days) recurs in subsequent cycles after dose reduction, the participant should come off protocol treatment.
- Participants who experience prolonged thrombocytopenia (platelets $< 75,000/\mu L$ for > 7 days) in the absence of hematopoietic involvement by Histiocytosis should have their dose of clofarabine reduced by 25% in subsequent cycles. If prolonged thrombocytopenia (platelets $< 75,000/\mu L$ for > 7 days) recurs in subsequent cycles, the participant should come off protocol treatment.
- If ANC or platelets counts are not recovered by day 42 in the absence of hematopoietic involvement by Histiocytosis, the participant should be taken off study.

6.3.2 Non-Hematologic Toxicity

- Participants who experience \geq grade 3 drug-related non-hematologic toxicity or asymptomatic grade 2 serum creatinine or serum total bilirubin during any clofarabine administration period should have clofarabine held until recovery to baseline or grade < 2 before resuming treatment at the same dose. Excluded from this rule are grade 3 skin rash, \geq grade 3 anorexia, transient isolated elevations in hepatic transaminases or alkaline phosphatase, and nausea/vomiting, diarrhea, or \geq grade 3 mucositis that resolves (with or without supportive care) to $<$ grade 3 within 48 hours of onset.

CONFIDENTIAL

This document is confidential. Do not disclose or use except as authorized.

7 DRUG FORMULATION AND ADMINISTRATION

Clofarabine Drug Information

[figure not shown]
7.1 Nomenclature

Chemical Name: 2-chloro-9-(2'-deoxy-2'-fluoro-β-D-arabinofuranosyl)-9H-purine-6-amine

Other names: CLOLAR, clofarabine; CAFdA; Cl-F-ara-A;
2-chloro-2'-fluoro-deoxy-9-β arabinofuranosyladenine
2-chloro-9-(2-deoxy-2-fluoro-β-D-arabinofuranosyl)adenine (Cl-F-ara-A)
2-chloro-2'-arabino-fluoro-2'-deoxyadenosine
2-chloro-2'-ara-fluorodeoxyadenosine (CAFdA)
2-chloro-2'-fluorodeoxyadenosine (CAFdA)

7.2 Molecular Structure

Figure 4-1: Molecular Structure

7.3 Description

Clofarabine is a white to off-white solid with a melting point of 228°C to 230°C and a molecular weight of 303.5. The drug substance is very stable in the dry state, and aqueous solutions are stable to heat treatment. Clofarabine is freely soluble in water (1.5 mg/mL) or buffered solutions at room temperature. Clofarabine is not less than 97% pure on a dried basis by high performance liquid chromatography (HPLC) analysis.

7.4 Form

Clofarabine is formulated at a concentration of 1 mg/mL. Clofarabine is supplied in 1 vial size: a 20-mL clear, glass vial with gray stopper and blue flip off seal. The 20-mL vials contain 20 mL (20 mg) of sterile solution. The pH range of the solution is 4.5 to 7.5. The solution is clear and practically colorless, preservative free, and free from foreign matter.

CONFIDENTIAL

This document is confidential. Do not disclose or use except as authorized.

7.5 Storage and Handling

Vials containing undiluted clofarabine for injection should be stored at controlled room temperature. The current commercial expiry period for Clolar (clofarabine) is 24 months at room temperature. Ongoing stability studies will continue to confirm the appropriate quality of drug product used for clinical trials beyond 24 months.

7.6 Preparation

Clofarabine should be filtered through a sterile 0.2 micron syringe filter and then diluted with 5% Dextrose or 0.9% Sodium Chloride prior to intravenous infusion to a final concentration between 0.15mg/ml and 0.4mg/ml. Clofarabine for injection should be diluted with 0.9% sodium chloride injection USP or European Pharmacopeia (EP) normal saline (NS) or 5% dextrose injection (D5W) USP or EP prior to IV infusion. The resulting admixture may be stored at room temperature but must be used within 24 hours of preparation. The dosage is based on the participant's body surface area (BSA), calculated using the actual height and weight before the start of each cycle and should not be adjusted downward to "ideal" weight. To prevent drug incompatibilities, no other medications should be infused concurrently through the same IV lines as clofarabine. Also, no blood products should be administered at the same time as clofarabine.

7.7 Handling

Qualified personnel, familiar with procedures that minimize undue exposure to themselves and the environment, should undertake the preparation, handling, and safe disposal of the chemotherapeutic agent in a self-contained and protective environment.

7.8 Availability

Clofarabine is an investigational agent in this study and will be supplied free-of-charge from Sanofi US Services Inc., on behalf of itself, and its affiliate, Genzyme Corporation

7.9 Administration

Clofarabine should be administered as I.V. infusion via peripheral or central access over 2-hours in a window of 1.5 to 2.5 hours.

7.10 Ordering

Clofarabine will be supplied by Sanofi US Services Inc., on behalf of itself, and its affiliate, Genzyme Corporation free of charge. The Coordinating Center will order the drug directly from Sanofi US Services Inc., on behalf of itself, and its affiliate, Genzyme Corporation. Each participating site will submit drug order requests using a specific drug order form supplied by the Coordinating Center. The completed form should be sent to: [contact].

CONFIDENTIAL

This document is confidential. Do not disclose or use except as authorized.

For US sites, allow 5-7 business days for initial drug orders and 3-5 business days for drug re-orders from the acknowledgement of order receipt to the date of delivery. For Canadian sites, allow 7-10 business days for initial and re-orders from the acknowledgement of order receipt to the date of delivery. There are no weekend, Monday, or Holiday deliveries. For questions regarding shipments, please contact [name] via email at [contact].

7.11 Accountability

Participating pharmacies will be required to submit Drug Accountability Logs at the time of monitoring documenting receipt and shipment of drug supply, dispensing/ordering of supply, and destruction of unused study medication and/or damaged or expired drug.

7.12 Destruction and Return

At the end of the study, unused supplies of clofarabine should be destroyed according to institutional policies. Destruction will be documented in the Drug Accountability Record Form.

8 STUDY CALENDAR

Baseline laboratory tests are to be conducted within 14 days prior to start of protocol therapy. Other evaluations (scans, pathology, EKG, etc.) must be done within 30 days of study entry. In the event that the participant's condition is deteriorating, laboratory evaluations should be repeated within 48 hours prior to initiation of the next cycle of therapy.

All assessments must be performed prior to administration of any study medication. All study assessments and medications should be administered within ± 3 days of the protocol-specified date, unless otherwise noted.

All follow-up assessments must be performed 12, 24, and 36 months from the off-treatment date (i.e. Day 28 of last administered cycle) ± 31 days.

A calendar for the time points when the required study data should be obtained is provided below.

CONFIDENTIAL

This document is confidential. Do not disclose or use except as authorized.

Table 2: Required Data / Study Calendar

Assessments	Baseline/ Screening (within 14 days)	Before Starting Each Cycle (within 3 days)	During Each Cycle	End of Cycle 2 ⁵	End of Treatment (+/- 7 days from day 28 of Cycle 6)	Follow- up ⁷ (+/- 31 days)
Informed Consent	X ¹					
Medical History Concurrent Condition Concomitant Medications/ Transfusions	X					
Height		X			X	
Weight		X			X	
BSA		X			X	
Physical exam/Vital Signs	X	X			X	
Performance Status	X ¹	X			X	
Hematology (CBC/Diff/Plts)	X ¹	X	Weekly ⁴		X	X ²
Electrolytes including Ca ⁺⁺ , PO ₄ , Mg ⁺⁺	X	X	Weekly ⁴		X	X ²
Creatinine, BUN, Serum glucose	X ¹	X	Weekly ⁴		X	X ²
LFTs (Total Protein/Alb., ALT, AST, ALP, Billi.)	X ¹	X	Weekly ⁴		X	X ²
Uric acid	X	X ²			X ²	
Serum β-HCG ³	X ¹				X	
EKG	X				X ²	
Urinalysis	X	X			X	
Bone Marrow Biopsy, Aspirate and Smear	X ² (within 30 days)			X ²	X ²	X ²
Disease Assessment/ Response Documentation (CT/MRI/ Bone Scan/ PET, as clinically indicated)	X ¹ (within 30 days)			X	X ⁶	X ⁸
Chest X-Ray PA and L	X				X	
Skeletal survey (stratum 1 only)	X			X	X ⁶	X ⁸
Clofarabine Administration			Days 1-5			
Adverse Event Assessment	X	X	Weekly ⁴		X	

¹ Source documents are required for eligibility review before registration.

² As clinically indicated.

³ For females of childbearing potential.

⁴ Weekly assessments are recommended as clinically indicated, to be completed every 7 days, +/- 3 days.

⁵ End of Cycle 2 assessments must be completed on Day 28 of Cycle 2 +/- 7 days, and prior to starting Cycle 3.

⁶ End of treatment disease assessment imaging window +/- 14 days from day 28 of Cycle 6.

⁷ All Follow-Up Assessments to be performed 12, 24, and 36 months from the off-treatment date (i.e. Day 28 of last administered cycle) +/- 31 days.

⁸ 12, 24, and 36 months after completion of therapy (i.e. Day 28 of last administered cycle)

CONFIDENTIAL

This document is confidential. Do not disclose or use except as authorized.

9 CRITERIA FOR RESPONSE – STRATUM 1

In contrast to leukemia or other malignancies the terms “remission” or “relapse” should be avoided. In accordance with the nature of Histiocytosis the following definitions should be applied to judge the effect of treatment. The response criteria stated below has been designed by the Histiocyte Society to be applied in therapeutic studies of LCH and should be used for therapeutic decisions.⁶⁸

Table 3: Definition of Disease State

Main Category	Sub-categories	Definition
Non-active Disease (NAD)		Resolution of all signs/symptoms (no evidence of disease)
Active Disease (AD)	Regressive Disease (Better)	Regression of signs/symptoms, and no new lesions.
	Stable Disease (Stable)	Persistence of signs or symptoms, and no new lesions.
	Progressive Disease* (Worse)	Progression of signs/symptoms and/or appearance of new lesions.

* Progression of skeletal lesions is defined as unequivocal enlargement of the size of existing lesions and/or appearance of new lesions.

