13.4 Evaluability

To be evaluable for inclusion in the analysis of response and toxicity, a patient must be eligible and have received at least one dose of protocol therapy. All evaluable participants must be assessed for response and toxicity to treatment, even if there are major protocol treatment deviations. Each participant should be assigned a category of response according to section 9 of the protocol.

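### End of Treatment assessment is dated only from Cycle 6, and 6.3.1 takes one toxicity subgroup off study: two wording conflicts affecting PFS and OS data from participants who stop early

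*Combined protocol and SAP*

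**What the plan says.** **End of Treatment.** The Table 2 column is headed "End of Treatment (+/- 7 days from day 28 of Cycle 6", and footnote 6 adds "End of treatment disease assessment imaging window +/- 14 days from day 28 of Cycle 6". Neither gives a date for someone who never reaches Cycle 6, although section 5 makes six cycles a maximum and 5.7 lists many reasons to stop sooner.

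**Follow-up.** Footnote 7 says "All Follow-Up Assessments to be performed 12, 24, and 36 months from the off-treatment date", and it defines that date as day 28 of the last administered cycle. Footnote 8, for disease assessment and skeletal survey, reads "12, 24, and 36 months after completion of therapy (i.e. Day 28 of last administered cycle". The section 8 text agrees. Section 5.6 adds "After completion of protocol therapy or removal from protocol therapy, participants will be followed for 3 years" (or until death).

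**Response assessment.** Section 13.4 says "All evaluable participants must be assessed for response and toxicity to treatment, even if there are major protocol treatment deviations", but sets no date for a participant who stops early.

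**Hematologic toxicity.** The first two bullets of 6.3.1 end with "the participant should come off protocol treatment". The third covers neutrophils or platelets not recovered by day 42 without hematopoietic involvement, and ends with "the participant should be taken off study".

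**Endpoints.** Sections 1.4a and 13.3 make PFS and OS secondary. Section 13.6 analyses them descriptively by Kaplan-Meier.

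**The concern.** Participants who stop early are the ones for whom the calendar has to be clear, and the plan expects some of them: 13.3c counts stopping for toxicity as a toxicity-event. Two passages do not fit the rest of the plan for these participants.

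First, the calendar serves them for follow-up but not for End of Treatment. Sites may improvise differently, and a disease assessment that was never made cannot be recovered at analysis. Progression would then be found later than in completers.

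Second, the protocol separates leaving therapy (5.7) from leaving the study (5.8). A site that follows the third bullet of 6.3.1 literally would stop collecting PFS and OS data because of toxicity. That is informative censoring if these participants fare differently from the rest.

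**Working it through.** The plan states no figure on this point, so there is none to reproduce. The check is date arithmetic plus a comparison of passages.

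**1. Scheduled gap between disease assessments**

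Inputs: cycles of 28 days, or 42 days with maximum delay (section 5); End of Cycle 2 assessment on day 28 of Cycle 2 (footnote 5); first follow-up 12 months, taken as 365 days, after day 28 of the last administered cycle *k* (footnotes 7 and 8). Visit windows are ignored.

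Day 28 of cycle *k* falls on study day (*k* − 1)L + 28, with L = 28 or 42. Gap = (day 28 of cycle *k*) + 365 − (day 28 of Cycle 2).

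| Stops after | L = 28 | L = 42 |
|---|---|---|
| Cycle 2 | 56 + 365 − 56 = 365 | 70 + 365 − 70 = 365 |
| Cycle 3 | 84 + 365 − 56 = 393 | 112 + 365 − 70 = 407 |
| Cycle 4 | 112 + 365 − 56 = 421 | 154 + 365 − 70 = 449 |
| Cycle 5 | 140 + 365 − 56 = 449 | 196 + 365 − 70 = 491 |

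With End of Treatment on day 28 of the last cycle, the longest gap is 365 days, as for completers. The Cycle 6 anchor therefore adds 28, 56 or 84 days (42, 84 or 126 with delays) for Cycles 3, 4 and 5, and nothing for Cycle 2.

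**2. Effect on 12-month PFS**

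Assumptions: exponential PFS, S(t) = 0.5^(t/median); a fraction *p* = 0.24 stops after Cycle 5; 28-day cycles; progression dated at the visit that finds it; 30.44 days per month. Such a participant's next scheduled assessment is on day 505 (month 16.6). Without an assessment at day 140 (month 4.60), a progression between the last check and day 140 is not counted by month 12.

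Excess = *p* × [S(last check) − S(4.60)].

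- *Last check at End of Cycle 2* (day 56, month 1.84), median 12: 0.24 × (0.899 − 0.767) = 3.2 points.
- *Last check before Cycle 5* (day 112, month 3.68), because 5.2 allows a cycle only without progression: 0.24 × (0.8085 − 0.7667) = 1.0 point.

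For medians of 24 and 60 months the ranges are 0.6 to 1.7 and 0.2 to 0.7 points. The 5.2 check is less sensitive than imaging, so the answer lies between the two ends.

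**3. Leaving therapy or leaving the study**

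- 6.3.1, bullets 1 and 2: recurrent prolonged cytopenia leads off protocol treatment.
- 6.3.1, bullet 3: counts not recovered by day 42 lead off study.
- 5.7, opening: failing the 5.2 criteria for the next cycle, which include the laboratory criteria of 3.1, is removal from protocol therapy.
- 5.6: removal from protocol therapy is followed by 3 years of follow-up.
- 5.7, first item: survival and disease status are followed for 3 years even after progression that requires systemic therapy.
- 5.8: five reasons for leaving the study (follow-up completed, death, loss to follow-up, withdrawal of consent for data submission, study completion). Count recovery is not among them.

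Bullet 3 stands alone against the other provisions. Read literally, it removes up to 36 months of PFS and OS follow-up.

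**4. When that would bias OS**

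Illustration only, since the documents give neither the number affected nor their prognosis. Let a fraction *p* be censored at *c* = 42/30.44 = 1.38 months, with death hazard *r* times that of the others, whose survival is S0.

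- True S(t) = (1 − p)S0(t) + p·S0(t)^r.
- Kaplan-Meier = [(1 − p)S0(c) + p·S0(c)^r] × S0(t)/S0(c).

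With *r* = 1 the two agree. With *r* = 2 and median OS of 60 months in the others, 24-month OS is too high by 0.7, 2.1 or 4.1 points for 1, 3 or 6 of 25. With a median of 24 months the excess is 0.9, 2.8 or 5.5 points.

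**The case against.** The strongest reply is that this is editorial. Follow-up is already anchored to the last administered cycle, so early stoppers keep their 12-, 24- and 36-month visits. Section 5.2 requires an examination and no progression before every cycle, and Table 3 defines progression by signs and symptoms as well as new lesions, so these participants are not unobserved after Cycle 2. Section 5.8 is the dedicated list for leaving the study and omits counts. Section 6 also speaks of an off-study visit, which suggests loose usage. Harm from 6.3.1 needs a site to follow one phrase over three sections.

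Most of this stands, and it keeps the point minor. It does not remove either conflict. No passage dates End of Treatment for someone who stops before Cycle 6. The opening of 5.7, the best answer to 6.3.1, is itself qualified awkwardly by a reference to the end of Cycle 2.

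Three stronger readings are not supported:

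- **That both passages cut PFS and OS follow-up.** The Cycle 6 anchor leaves one assessment undated. It shortens no follow-up, and OS does not depend on it.
- **That Rule B's 6 of 25 caps the number taken off study.** Rule B says what is accepted as deliverable, not what can occur. Section 13.5 defines unacceptable toxicity through grade 5 and non-hematological events, so it is unclear whether stops for low counts enter the rule.
- **That annual visits make the PFS curve unreliable.** That spacing applies equally to completers, 13.3a dates PFS at first occurrence, and no 12- or 24-month figure is planned.

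**Conclusion.** Both conflicts are real and minor.

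The Cycle 6 anchor lengthens one assessment interval from at most 365 days to 393, 421 or 449 days (407, 449 or 491 with maximum delays) for non-progressing participants who stop after Cycle 3, 4 or 5. The effect on 12-month PFS is about 1.0 to 3.2 points under the assumed 24% stopping after Cycle 5 and 12-month median, and smaller with longer medians or fewer stoppers.

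The wording in 6.3.1, read literally, ends PFS and OS follow-up only for participants without hematopoietic involvement whose counts have not recovered by day 42. OS is biased only if their prognosis differs. The documents do not give their number, so no size can be claimed beyond the illustration.

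The primary endpoint is judged up to the End of Cycle 2 assessment, which has its own date, and 13.4 keeps every evaluable participant in the response analysis. Rule A is unaffected.

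**What to change.** 1. In the Table 2 End of Treatment column head and footnote 6, replace the Cycle 6 anchor with day 28 of the last administered cycle, as footnotes 7 and 8 already do. The cost is a few words and one disease assessment that completers already have. After Cycle 2 none is added, because it coincides with the End of Cycle 2 assessment. The 12-month spacing after treatment does not change.

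2. Reconcile the third bullet of 6.3.1 with 5.6, 5.7 and 5.8, so that its wording does not end PFS and OS follow-up for these participants. This concerns data collection only and leaves the treatment rule as it is. The cost is a few words, plus follow-up that 5.6 already requires after removal from protocol therapy.
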